4.9.5 Deaths

All deaths recorded on the AE page of the CRF will be considered a death in the analyses. Any deaths that occur during the study will be described in depth as narrative in the CSR. Deaths with an onset from day 1 of the double-blind treatment period up to and including 30 days after the last dose date will be considered as occurring during the double-blind treatment period.

Summaries of deaths will include data regardless of use of rescue medication; listing of deaths will also include all data regardless of use of rescue medication (Enrolled population).

4.9.6 Hypoglycaemia

Hypoglycaemic events occurring after the start of double blind study medication up to and including 4 days after the last double-blind dosing date will be considered as obtained during the double-blind treatment period and included in the summaries described below.

The proportion of patients with hypoglycaemic events and the number of hypoglycaemic events per patient will be summarised by treatment group. Hypoglycaemic events will also be categorised as follows:

• Major hypoglycaemic events: symptomatic events requiring external assistance due to severe impairment in consciousness or behaviour, with a capillary or plasma glucose

value <54 mg/dL (<3.0 mmol/L), and prompt recovery after glucose or glucagon administration

- Hypoglycaemia: Typical symptoms of hypoglycaemia accompanied by blood glucose \leq 70 mg/dL (3.9 mmol/L)
- Other episodes of hypoglycaemia: Symptoms of hypoglycaemia without a blood glucose reading or symptoms of hypoglycaemia accompanied by blood glucose >70 mg/dL (3.9 mmol/L)
- Confirmed hypoglycaemia: Typical symptoms of hypoglycaemia accompanied by blood glucose ≤50 mg/dL (2.8 mmol/L)
- Asymptomatic hypoglycaemia: An event not accompanied by typical hypoglycaemia symptoms but with measured plasma glucose \leq 70 mg/dL (\leq 3.9 mmol/L)

Hypoglycaemic events leading to discontinuation of study medication will be summarised by treatment. A summary of hypoglycaemic events over time by treatment will also be provided.

Summaries will be produced using data obtained prior to rescue medication only then repeated using all data regardless of use of rescue medication for patients in the Safety Analysis Set. A listing of patients will be produced for all hypoglycaemic events.

4.9.7 Laboratory evaluation

Unless otherwise specified, laboratory data obtained after the start of study medication and up to and including 4 days (or 30 days for liver function laboratory test) after the last dose of the double-blind treatment period, will be considered as obtained during the double-blind treatment period.

Laboratory data (including haematology, clinical chemistry, creatinine and lipids; Appendix III) will be summarised by visit using the analysis windows defined in Table 12. Values and changes from baseline for laboratory data will be summarised by treatment group at each scheduled visit during the double blind treatment period using descriptive statistics (using all available data regardless of use of rescue medication) for patients in Safety Analysis Data Set. Summaries of laboratory data will be produced for the double-blind treatment period, while listings will include values from the follow-up visit.

4.9.7.1 Marked laboratory abnormalities

Laboratory abnormalities will be evaluated based on marked abnormality values (MA). The pre-defined criteria for marked abnormalities are detailed in Appendix III, Table 15. If both the baseline and on-treatment values of a parameter are beyond the same MA limit for the parameter, then the on-treatment value will be considered an MA only if it is more extreme (farther from the limit) than was the baseline value. If the baseline value is beyond the low MA limit, and the post-baseline value is beyond the high MA limit (or vice-versa), then the post-baseline value will be considered a MA.

Laboratory abnormalities during the double-blind treatment period will be summarised using all data regardless of use of rescue medication.

Additionally, patients with MA will be listed.

4.9.7.2 Additional laboratory data summaries

Shift tables will be produced for the following parameters (including all data regardless of use of rescue medication):

- Sodium, calcium, phosphorus and magnesium baseline to highest category of Low, Normal or High
- Sodium, potassium and calcium baseline to lowest category of Low, Normal or High
- Urinary Albumin to Creatinine Ratio (UACR) for categories of albuminuria (normal (0-<30mg/g), micro(30-,300 mg/g), macro(≥ 300 mg/g))

For liver safety, a summary of the proportion of patients with elevated liver tests including elevated AT (ALT and/or) AST) and total bilirubin will be provided. The following three criteria will be summarised:

- (AST or ALT > 3XULN) and (Bilirubin > 1.5XULN within 14 days on or after AT elevation)
- (AST or ALT > 3XULN) and (Bilirubin > 2XULN within 14 days on or after AT elevation)
- (AST or ALT > 3XULN) and {(Bilirubin > 2XULN and no ALP >= 2XULN) within 14 days on or after AT elevation)}

4.9.8 Vital signs

Vital signs data obtained after the start of study medication dosing up to and including 4 days after the last double-blind dosing date will be considered as obtained during the double-blind treatment period.

Vital sign measurements include systolic and diastolic blood pressure and pulse are measured with the patient in a sitting position.

Vital signs data will be summarised by visit using the visit windows defined in Table 12. Values and changes from baseline for vital sign measurements will be summarised by treatment group at each scheduled visit during the double-blind treatment period using descriptive statistics (using all available data regardless of use of rescue medication) for patients in Safety Analysis Data Set.

4.9.9 Electrocardiograms

The normality/abnormality of the ECG tracing (as determined by the investigator) will be summarised using frequency tables on number of patients with a normal/abnormal ECG

tracing at baseline versus week 52 of the double-blind treatment period. When the data at week 52 is not available for a patient, the last observation prior to week 52 of that patient will be used in the summary.

A listing of patients will be produced which will display all ECG findings up to week 52 in patients with abnormal ECGs (as determined by the investigator).

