HbA1c	×	×	×	×	×	×	×	×	×	×	×	×	X	
Creatinine (to calculate CrCl and eGFR)		×	×	×	×	×	×	×	×	×	×	×	×	×
FPG (local laboratory)			X	X	X	X	×	X	X	X	X	X	X	
FPG (central laboratory)		X	X	X	X	X	×	X	X	X	X	X	X	X
$Lipids^h$		X	X										X	X
C-peptide		×												
Hepatitis screening paneli		×												
TSH		X												
Urinalysis		X	X	X	X	X	X	X	X	X	X	X	X	X
Pregnancy test (urine, WOCBP only)		X	X	X	X	X	X	X	X	X	X	×	X	X
Hypoglycaemic events		X	X	X	X	X	×	X	X	X	X	X	X	X
Discuss individual targets for glucose control (FPG and HbA1c)			×											
AEs/SAEs		×	×	×	×	×	×	×	×	×	×	×	X	×

						64	L D. L.	1. 1.15		1				
	Screening	Enrolment	R/ Baseline				27-Week Double-Dillid Treatment Feriod	ne-Dillia			=		EOT/ Rescue ^a	Safety Follow-up
Visit	$\mathbf{S}_{\mathbf{p}}$	1	2°	3	4	S	9	7	∞	6	10	11	12	13
Weeks	-3	-2	0	2	4	9	∞	10	12	24	36	48	52	55
Visit window (days) ^d	±3	#3	-	±3	#3	#3	±3	#3	±3	+ 4	+ 4	+ 4	7=	#7
Diet and lifestyle advice		×	×	×	×	X	×	×	X	×	X	×	X	
Dispense glucometer and/or supplies; provide instructions		×	X	×	×	×	×	×	×	×	×	×		
Dispense patient diary		X	X	X	X	X	X	X	X	X	X	X		
Dispense study medication			×	×	×	×	×	×	×	×	×	×		
Register actual glimepiride dosage in IWRS				×	×	×	X	×	×	×	×	×	×	
Patient diary review for glucometer values/hypoglycaemic events			X	×	×	×	×	×	×	×	X	×	X	
Perform SF-36 survey			X							X			X	
Perform Hypoglycaemia Fear Survey-Worry Scale			×							×			X	
Perform IWQOL-Lite			X							X			X	
Collect unused study medication/supplies													X	×
Dispense rescue medication (if necessary)					×	×	×	×	×	×	×	×	×	

Early Termination procedures are to be completed for all patients who terminate the study or are rescued before Visit 12 (Week 52) of the Treatment Period. An optional Screening visit (Visit S) may occur within 1 week prior to Enrolment (Visit 1) to screen for eligibility based on a non-fasting sample of HbA1c density lipoprotein, IWQOL Impact of Weight on Quality of Life, IWRS Interactive Web Response System, LDL low-density lipoprotein, R randomisation, electrocardiogram, eGFR estimated glomerular filtration rate, EOT end of treatment, FPG fasting plasma glucose, HbA1c haemoglobin A1c, HDL high-Abbreviations: AE adverse event, Base baseline, BP blood pressure, BMI body mass index, CrCl creatinine clearance, E-code enrolment code, ECG SAE serious adverse event, SF short form, TSH thyroid stimulating hormone, WOCBP women of child-bearing potential.

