4.5 Definitions

4.5.1 Baseline values

For all efficacy variables, the baseline value will be the last non-missing value on or prior to the first dose of the double-blind study drug date or the last non-missing value of the visit 1 or visit 2 assessment for those subjects without a first dose start date.

The baseline value of each safety laboratory test or physical exam endpoint is defined as the last assessment (either numerical or character value) on or prior to the first dose of double-blind study drug date or the last non-missing value of the visit 1 or visit 2 assessment for those subjects without a first dose start date.

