4.6.2 Handling missing efficacy data

Missing data can result from patients discontinuing the study prematurely or by missing intermediate visits or selected assessments while remaining in the study. To eliminate missing data, every effort will be made to obtain the protocol-required data for all scheduled study assessments for all enrolled patients. For efficacy analyses, the MMRM model assumes missing observations are missing at random (MAR). MAR means that the tendency of a data value to be missing depends only on the observed data, and not on the missing data. For example, if an HbA1c value is missing, it assumes this is not related to the missing data but to some of the observed data (response and covariates) (Ref (1)).

For the change in HbA1c and weight analyses using MMRM, values recorded after rescue treatment for those patients who used rescue medication or values collected more than 8 days after the last dose date for patients who stayed more than 8 consecutive days off treatment are excluded from the analysis. For the change in FPG analysis using MMRM, values recorded after rescue treatment for those patients who used rescue medication or values collected more than 1 day after the last dose date for patients who stayed more than 1 consecutive days off treatment are excluded from the analysis. For the change in SBP analysis using MMRM, values recorded after rescue treatment for those patients who used rescue medication or values collected more than 4 days after the last dose date for patients who stayed more than 4 consecutive days off treatment are excluded from the analysis.

The MMRM model assumes the time course of the endpoint values for patients who discontinue double-blind treatment or are rescued at a specific time point is consistent with the time course for patients ongoing at that time point.

Summaries of missing data by visit for HbA1c will be provided in order to explore this assumption (see Table 16 provided in Appendix IV).

When performing ANCOVA, the Last Observation Carried Forward (LOCF) method will be used for dealing with missing values i.e. if no Week 52 measurement is available, the last available earlier post-baseline measurement will be used except for the efficacy variable time spent below HbA1c target. For patients who started rescue medication prior to Week 52, their last post-baseline measurement taken prior to the date of the first dose of rescue medication will be used.

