4.11.2 Visit Windows

Deviations are to be expected between patients in the actual number of study days from randomisation to when planned visits are carried out. To handle these deviations in tables, figures, listings, and analyses, visit assessments will be slotted according to visit windows. Data will be assigned to the visit windows using study day. For the efficacy and safety data, the data will be listed and summarised by visit as listed in Table 12 below:

Table 12. Visit windows for efficacy and safety data

Visit	Target	Adjusted windows for analyses (Days)			
	Day	HbA1c	Vital Signs, sBP Body Weight, FPG*, urinalysis hypoglycaemic events	Waist circumference, BMI, ECG, complete physical examination**	Laboratory parameters***, Serum lipids
Baseline	1	≤1	≤1	≤1	≤1
Week 2	15	2 - 21	2 - 21		
Week 4	29	22 - 35	22 - 35		
Week 6	43	36 - 49	36 - 49		
Week 8	57	50 - 63	50 - 63		
Week 10	71	64 - 77	64 - 77		
Week 12	85	78 - 126	78 - 126		
Week 24	169	127 - 210	127 - 210		
Week 36	253	211 - 294	211 - 294		
Week 48	337	295 - 348	295 - 348		
Week 52	365	349 - Last dosing date ⁴ + 7	349 - Last dosing date [¥] + 4*	2 – Last dosing date of the DB period + 4	2 – Last dosing date of the DB period + 4
Follow-up Week 55	386	(Last dosing date $^{4} + 7$) – Last visit date	(Last dosing date [‡] + 4*) – Last visit date		(Last dosing date $^{\frac{1}{4}} + 4$) – Last visit date

^{*:} For FPG, week 52 and week 55 windows use last dosing date +1.

^{**:} also assessed at Week 24; **: clinical chemistry parameters also assessed at Weeks 12, 24, 36, 48.

[¥]: Last dosing date ≥ Day 349

In case of multiple observations within a single visit window, the following rules apply:

- If there are two or more observations within the same visit window, the non-missing observation closest to the target day will be used in the analysis
- If two observations are equidistant from the target day, the non-missing observation with the later collection date will be used in the analysis
- If two observations are collected on the same day and have a collection time associated with them, the non-missing observation with the later collection time will be used in the analysis
- If two or more observations are collected on the same day, all non-missing but with no collection time associated with at least one of them, the average of the observations will be used in the analysis.

If a visit window does not contain any observations, the data will be missing for that visit.

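### The fallback for a missing week 52 ECG in SAP 4.9.9 is either redundant or carries the baseline ECG forward, because it does not require a post-baseline value

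*SAP*

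**What the plan says.** Section 4.9.9 compares the investigator's normal/abnormal reading of the "tracing at baseline versus week 52 of the double-blind treatment period". For gaps it adds: "When the data at week 52 is not available for a patient, the last observation prior to week 52" is used. No lower limit is put on how early that observation may be.

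Four other parts of the SAP bear on this rule:

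- **Schedule (section 1.2, Table 1).** The 12-lead ECG is marked at enrolment (Visit 1), baseline (Visit 2) and the end-of-treatment/rescue visit (Visit 12). A table note adds: "Early Termination procedures are to be completed for all patients who terminate the study or are rescued before Visit 12".
- **Analysis window (section 4.11.2, Table 12).** The column headed "Waist circumference, BMI, ECG, complete physical examination" has a baseline window of Day 1 or earlier and a single post-baseline window, labelled week 52: "2 – Last dosing date of the DB period + 4".
- **Limit after last dose (sections 4.9 and 4.11.3).** Safety measurements other than liver tests enter the summaries only up to the 4th day after the last blinded dose.
- **Carry-forward for efficacy (section 4.6.2).** Here the restriction is written out: "the last available earlier post-baseline measurement will be used".

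**The concern.** A carry-forward rule in a baseline-versus-follow-up table should draw only on follow-up data. If it can reach back to baseline, the baseline result is cross-tabulated against itself. The patient then lands on the diagonal as unchanged without ever having been re-examined.

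ECG is one of the safety objectives in section 1.1.4, and planned table 105 is its only planned summary table. Filling cells this way would understate shifts in both directions (normal to abnormal and abnormal to normal). It would also hide how many patients had no ECG on treatment.

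**Working it through.** The SAP states no figure for this table, so there is none to reproduce. The check sets the rules side by side and then scales the effect under stated assumptions.

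**Step 1: when does the fallback operate?** Only when week 52 is empty. By Table 12, week 52 is empty only if the patient has no ECG from Day 2 to last dose + 4.

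**Step 2: what can it then select?** An ECG before week 52 and outside that window is either on or before Day 1, or more than 4 days after the last dose. The second kind is barred by 4.9 and 4.11.3. That leaves Day 1 or earlier, which Table 12 classes as baseline. Section 4.5.1 similarly places baseline for laboratory and physical-examination endpoints "on or prior to the first dose of double-blind study drug date".

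**Step 3: example patients** (enrolment ECG on Day -13 and baseline ECG on Day 1 in every row)

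| Post-baseline ECG | Last dose | Result |
|---|---|---|
| Day 365 | Day 365 | Week 52 window; fallback not used |
| Rescue ECG Day 120, none later | Day 200 | Week 52 window (Day 120) |
| Unscheduled Day 90 only | Day 365 | Week 52 window (Day 90) |
| Early termination Day 123 | Day 120 | Week 52 window (120 + 4 = 124) |
| Early termination Day 135 | Day 120 | Outside window and barred by the 4-day limit; fallback takes baseline |
| None | Day 120 | Fallback takes baseline |

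The same rules were run over last-dose days from 1 to 365 in steps of 7, with one post-baseline ECG on any day from 2 to 371. The fallback selected an on-treatment ECG in 0 cases, as Step 1 implies.

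**Step 4: other text on ECG timing.** Section 1.2.4.2 loosely says that baseline-listed parameters are assessed at Visits 3 to 11, which Table 1 does not show for ECG. Any such ECG taken by last dose + 4 would fall in the week 52 window, so the result is the same.

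**Step 5: size.** Let p be the true shift rate in patients with an on-treatment ECG, q the unobserved rate in those without one, and m the fraction without one.

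- Rate shown in the table: p(1 − m), because every carried-forward patient counts as no shift.
- True rate: p(1 − m) + qm.
- Shortfall: qm.

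None of the three is given in the SAP. Assuming p = q = 5%:

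| m | Shown | Shortfall |
|---|---|---|
| 5% | 0.05 × 0.95 = 4.75% | 0.25 points |
| 10% | 0.05 × 0.90 = 4.50% | 0.50 points |
| 15% | 0.05 × 0.85 = 4.25% | 0.75 points |

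Assuming p = q = 10% instead, m = 5% and 10% give 9.5% and 9.0%. With carried-forward patients outside the denominator, the table shows p(1 − m)/(1 − m) = p.

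**The case against.** The best defence is that the 4.9.9 sentence and the Table 12 window describe one rule. Patients who stop or are rescued early should have an ECG at that visit. That ECG is the last one before week 52, and the wide window is how it gets used. On this reading nothing instructs anyone to carry baseline forward. Section 4.9 limits safety summaries to the double-blind period and change-from-baseline analyses to patients with data at both points. Section 4.1 provides a missing category outside the denominators.

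Much of this stands. The sentence may well have been meant that way, and a careful programmer could reach the sensible result. But on that reading the sentence adds nothing to Table 12, and it still does not exclude baseline for a patient with no later ECG. The both-values rule in 4.9 gives way where another section specifies otherwise, which 4.9.9 can be taken to do. The missing category in 4.1 applies only when appropriate, and a filled cell is no longer missing.

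Two stronger readings are tempting:

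- **That ECGs taken well after stopping drug would be reported as week 52 results.** Sections 4.9 and 4.11.3 exclude them. Even if 4.9.9 were taken to override that limit, such an ECG could show a change, so it would not necessarily be counted as unchanged.
- **That abnormalities are hidden.** Section 4.9.9 also requires a listing of all ECG findings up to week 52 in patients with abnormal ECGs, so an observed abnormality remains visible.

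**Conclusion.** The rule is badly fixed. Under the SAP's own windows it is either redundant or carries the baseline ECG forward, and its wording does not rule out the second. Taken literally, it counts patients with no on-treatment ECG as unchanged and keeps them in the denominator.

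The effect is modest and its true size is unknown. The 0.25 to 0.75 point shortfall rests on an assumed 5% shift rate, the same in patients without an ECG, and on 5% to 15% of patients lacking one. Because early-termination and rescue visits include an ECG, the affected group is limited to patients who miss that ECG or have it more than 4 days after the last dose, with no other on-treatment ECG.

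A reader might also infer a distorted comparison between arms. That would need ECG missingness to differ by arm, which the document gives no ground to assume. The table is descriptive, section 4.9 plans no formal safety testing, and no endpoint or decision depends on it. This is a minor correction.

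**What to change.** Replace the fallback sentence in 4.9.9 with wording such as: if no week 52 ECG is available, only the last post-baseline ECG taken up to 4 days after the last double-blind dose is used; patients with no such ECG are shown as missing and do not count in the denominator, as in section 4.1. A cross-reference to Table 12 would make clear that this is the same window and that its rule for multiple observations applies.

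The cost is one sentence in the SAP, one added row or column in planned table 105, and slightly smaller denominators. No new data are needed. Leaving these patients out still assumes that they resemble those with an ECG, but the missing count lets the reader judge how much that matters.

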4.9.10 Pregnancy test results

A by-patient listing of pregnancy test results will be provided using the Safety Analysis Set.

4.10 Figures and graphs

The following figures will be presented by treatment group.

- Longitudinal plots
 - HbA1c adjusted mean change from baseline over time
 - o Total body weight adjusted mean change from baseline over time
 - o FPG adjusted mean change from baseline over time
- Forest plots
 - o HbA1c adjusted mean change from baseline to week 52
 - o Total body weight adjusted mean change from baseline to week 52
 - Proportion of patients reporting at least one episode of confirmed hypoglycaemia from baseline until week 52
- Kaplan-Meier curves for:
 - o Time to rescue
 - Time to discontinuation of study medication
- Spaghetti plot
 - o Mean HbA1c over time grouped by last available visit on treatment
- Dot plot (showing relative risk) for:
 - Most common Adverse Events, by preferred term

4.11 Conventions

4.11.1 Study Day

If the date of assessment is prior to first dose of study medication then study day will be calculated as:

Study day = Date of assessment - Date of first dosing.

If the date of assessment is on or after the day of first dose then study day will be calculated as:

Study day = Date of assessment – Date of first dosing + 1

Day 1 of the double-blind treatment period is the start date of double-blind study medication.

4.11.2 Visit Windows

Deviations are to be expected between patients in the actual number of study days from randomisation to when planned visits are carried out. To handle these deviations in tables, figures, listings, and analyses, visit assessments will be slotted according to visit windows. Data will be assigned to the visit windows using study day. For the efficacy and safety data, the data will be listed and summarised by visit as listed in Table 12 below:

Table 12. Visit windows for efficacy and safety data

Visit	Target	Adjusted windows for analyses (Days)			
	Day	HbA1c	Vital Signs, sBP Body Weight, FPG*, urinalysis hypoglycaemic events	Waist circumference, BMI, ECG, complete physical examination**	Laboratory parameters***, Serum lipids
Baseline	1	≤1	≤1	≤1	≤1
Week 2	15	2 - 21	2 - 21		
Week 4	29	22 - 35	22 - 35		
Week 6	43	36 - 49	36 - 49		
Week 8	57	50 - 63	50 - 63		
Week 10	71	64 - 77	64 - 77		
Week 12	85	78 - 126	78 - 126		
Week 24	169	127 - 210	127 - 210		
Week 36	253	211 - 294	211 - 294		
Week 48	337	295 - 348	295 - 348		
Week 52	365	349 - Last dosing date ⁴ + 7	349 - Last dosing date [¥] + 4*	2 – Last dosing date of the DB period + 4	2 – Last dosing date of the DB period + 4
Follow-up Week 55	386	(Last dosing date $^{4} + 7$) – Last visit date	(Last dosing date [‡] + 4*) – Last visit date		(Last dosing date $^{\frac{1}{4}} + 4$) – Last visit date

^{*:} For FPG, week 52 and week 55 windows use last dosing date +1.

^{**:} also assessed at Week 24; **: clinical chemistry parameters also assessed at Weeks 12, 24, 36, 48.

[¥]: Last dosing date ≥ Day 349

In case of multiple observations within a single visit window, the following rules apply:

- If there are two or more observations within the same visit window, the non-missing observation closest to the target day will be used in the analysis
- If two observations are equidistant from the target day, the non-missing observation with the later collection date will be used in the analysis
- If two observations are collected on the same day and have a collection time associated with them, the non-missing observation with the later collection time will be used in the analysis
- If two or more observations are collected on the same day, all non-missing but with no collection time associated with at least one of them, the average of the observations will be used in the analysis.

If a visit window does not contain any observations, the data will be missing for that visit.

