4.4 Sensitivity analyses

Sensitivity analyses will be carried out for the primary efficacy endpoint (change in HbA1c from baseline (week 0) to week 52) only. These sensitivity analyses will be as follows

- Mixed Model Repeated Measures (MMRM) using the Per-Protocol analysis set,
- ANCOVA using values prior to rescue treatment (LOCF will be used if the week 52 value is not available)
- The MMRM model will be repeated including all values according to the ITT principle (i.e. all values will be included regardless of use of rescue treatment or treatment discontinuation)

Further details of these sensitivity analyses is provided in Section 4.8.4.

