4.11.3 Post-Dosing Observations

While double blind treatment period efficacy and safety observations will be listed regardless of whether the patient was taking blinded study drug, observations will be summarised only when the following rules are satisfied:

For efficacy parameters

- HbA1C, body weight, BMI and waist circumference will be summarised only if measured on or before the 8th day after the last double-blind drug dosing date.
- FPG, will be summarised only if measured on or before the first day after the last randomised, double-blind drug dose date.
- SBP will be summarised only if measured on or before the 4th day after the last double-blind drug dosing date.

For safety parameters

- SAEs and the lab measurements for the liver function tests will be included in the summaries only if occurred/measured on or prior to the 30th day after the last blinded drug treatment date.
- All other safety events (non-severe AEs, hypoglycaemia, etc.) and measurements (safety lab, vital signs, etc.) will be included in the summaries only if occurred/measured on or prior to the 4th day after the last blinded drug treatment date.

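### Table 12 ties the end of the Week 52 window to the last dose, so the all-values HbA1c model drops observed Week 52 values of patients who stopped drug; its limits are also tighter than the SAP's own 8-day cut-off

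*SAP*

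**What the plan says.** **Slotting rule.** SAP 4.11.2 applies its windows to analyses as well as displays: "To handle these deviations in tables, figures, listings, and analyses, visit assessments will be slotted according to visit windows". If a window is empty, "If a visit window does not contain any observations, the data will be missing for that visit". In Table 12 the Week 52 HbA1c window is "349 - Last dosing date" + 7. Weight shares a column with vital signs that ends at last dose + 4, and BMI and waist also end at + 4. A footnote to the last dosing date reads "Last dosing date ≥ Day 349". The windows for Weeks 2 to 48 carry no last-dose limit.

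**All-values model.** SAP 4.4 and 4.8.4, Table 11 and planned table 24 describe a repeat of the primary MMRM in which "all values will be included regardless of use of rescue treatment or treatment discontinuation". The notes to Table 16 (Appendix IV) say that patients who stopped drug may still have an HbA1c. They count only patients lost to follow-up or without a baseline as excluded from this model.

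**Off-drug cut-offs.** SAP 4.11.3 states that HbA1c, weight, BMI and waist "will be summarised only if measured on or before the 8th day after the last double-blind drug dosing date". The 8-day rule also appears in 4.6.2 (HbA1c and weight), 4.8.1 (HbA1c) and 4.8.2 (all four). For the other two variables, Table 12 and the cut-off agree: "For FPG, week 52 and week 55 windows use last dosing date +1", and "SBP will be summarised only if measured on or before the 4th day after the last double-blind drug dosing date".

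**The concern.** The MMRM treats week as a category, so a value enters only if it has a visit slot. For a patient who stopped drug well before Week 52, Table 12 offers no Week 52 slot, and no other section supplies one. The analysis meant to show the non-inferiority result regardless of discontinuation would then predict Week 52 under missing-at-random for these patients, even where the endpoint was measured.

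Separately, two rules for the same on-treatment data disagree. If both are applied, the narrower one governs. Some Week 52 values that the 8-day cut-off would admit are then lost from the primary HbA1c analysis, the key secondary weight analysis, and BMI and waist.

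**Working it through.** **Inputs from the SAP.** Week 52 target Day 365 and Table 12 limits (4.11.2); Visit 12 window of ±7 days (Table 1), so Days 358 to 372; 8-day cut-off (4.6.2, 4.8.1, 4.8.2, 4.11.3); SD 1.0% and margin 0.30% (1.3). The SAP gives no figure of its own for this point, so there is none to reproduce.

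**1. Who gets a Week 52 HbA1c slot.** Let L be the last-dose day and d the assessment day. Table 12 requires 349 ≤ d ≤ L + 7 and, by the footnote, L ≥ 349.

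- L ≤ 341: L + 7 ≤ 348, so the window is empty even without the footnote.
- L from 342 to 348: the footnote empties it.
- A value on d = 365 needs L ≥ 365 − 7 = 358. For visits on Days 358 and 372 the minimum L is 351 and 365.

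Example: last dose on Day 200, HbA1c on Days 253, 337 and 365. The first two fall in the Week 36 (211–294) and Week 48 (295–348) windows. The third has no Week 52 slot. With L = 350, the Day 365 value falls in the follow-up window, which starts at 350 + 7 = 357.

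This takes 4.8.4 as lifting the general 4.11.3 restriction for this model, so earlier off-drug values stay in. Rescued patients who remain on blinded drug keep their Week 52 slot.

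**2. Table 12 against the 8-day cut-off.**

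| Variable | Table 12 limit | Cut-off | Days lost |
|---|---|---|---|
| HbA1c | L + 7 | L + 8 | +8 |
| Weight, BMI, waist | L + 4 | L + 8 | +5 to +8 |
| SBP | L + 4 | L + 4 | none |
| FPG | L + 1 | L + 1 | none |

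For a Day 365 visit, the 8-day rule needs L ≥ 357. Table 12 needs L ≥ 358 for HbA1c and L ≥ 361 for weight. With L = 364, a visit on Days 369 to 372, still inside the Visit 12 window, loses weight; one on Day 372 also loses HbA1c.

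For HbA1c and weight the footnote adds a further loss. For L = 341 to 348, the days from 349 to L + 8 number 1, 2, …, 8, so 1 + 2 + … + 8 = 36 day pairs meet the 8-day rule. None gets a slot. One such pair is HbA1c on Day 350 after a last dose on Day 345.

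**3. Illustrative size of part 1.** The following are assumptions, not SAP figures: 10% stop in control and 15 to 25% in a test arm, evenly over Days 1 to 348; 0.5 to 1.0% of HbA1c effect is lost over 90 days; Week 48–52 correlation ρ is 0.79 to 0.94; there is no true on-treatment difference.

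Hand check with all stoppers still measured and a linear loss. The mean fraction of the loss reached is 0.914 by Day 365 and 0.838 by Day 337. Per stopper, the part not recovered from the Week 48 value is about 0.914 − ρ × 0.838, which is 0.126 at ρ = 0.94 and 0.252 at ρ = 0.79. Multiply by the loss and by the difference in stopping rates:

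- smallest: 0.126 × 0.5 × 0.05 = 0.003%
- largest: 0.252 × 1.0 × 0.15 = 0.038%

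A simulation (200,000 patients per arm, 10 visits, unstructured MMRM) compared all values with Week 52 dropped for stoppers:

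| Stoppers still measured | Hidden shift | Share of 0.30% |
|---|---|---|
| All | 0.0030–0.0374% | 1–12.5% |
| Half | 0.0017–0.0223% | 0.6–7.4% |
| A quarter | 0.0009–0.0122% | 0.3–4.1% |

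The full all-values shift in these scenarios is 0.023 to 0.137%. With equal stopping rates and equal loss the hidden part is zero within simulation noise (0.002%). With the rates reversed, all stoppers measured, it is −0.0028 to −0.0374%.

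**The case against.** The strongest reply is that the promise to include all values is the specific rule and should override the general Table 12, just as it is taken to override 4.11.3. That reading probably matches the intent. It lifts an exclusion, but it does not say which days count as Week 52 for a patient off drug, and the SAP gives no other window. A programmer would have to invent one.

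Second, the SAP does not say that patients who stop drug keep attending visits; continuation on the original schedule is stated only for rescued patients. If few are measured at Week 52, little is lost. This stands as a limit on size. Against it, Table 16 foresees HbA1c values after stopping, and 4.6.2 promises every effort to collect scheduled data.

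Third, the footnote mark in the HbA1c cell is damaged in the extracted text, so its link to the Day 349 condition is inferred. The + 7 limit does not depend on it; most of the Day 341–348 argument does. Those values fall on Days 349 to 356, before the scheduled Visit 12, so mainly early-termination visits are affected.

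Fourth, the Day 364 example assumes dosing ended 5 to 8 days before the visit, which nothing in the SAP says is common. That is fair. It shows which days are lost, not how often.

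**Conclusion.** The point holds. As written, the all-values MMRM cannot use an off-drug Day 365 HbA1c unless the last dose was on Day 358 or later, which contradicts its stated purpose. It still differs from the primary analysis, because post-rescue values and off-drug values up to Day 348 enter. Table 12 also conflicts with the 8-day cut-off for HbA1c, weight, BMI and waist.

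The consequence is limited. The primary analysis excludes values more than 8 days off drug anyway, so the non-inferiority decision does not change through the all-values gap, and that model is one of three sensitivity analyses with no decision rule attached. Its size depends on discontinuation and retention rates that the SAP does not give. The illustrative range of 0.001 to 0.037% rests wholly on the assumptions listed, apart from the SD and margin, and its sign depends on which arm stops more.

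For the on-treatment mismatch no effect size can be given. It does reach primary HbA1c and key secondary weight, but completers who dosed to within 4 days of Visit 12 are unaffected. This should be corrected before unblinding.

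**What to change.** 1. For the all-values MMRM, assign HbA1c to Week 52 by study day alone: from Day 349 to a fixed day that covers the Visit 12 window (Days 358 to 372), taking the value closest to Day 365. Day 375 is one possible upper limit; Table 1 schedules no HbA1c at Visit 13, so no planned value competes.
2. State in 4.8.4 that the last-dose limits of Table 12 and 4.11.3 do not apply to this analysis.
3. For the on-treatment analyses, set the Week 52 upper limit in Table 12 to last dose + 8 for HbA1c, weight, BMI and waist. Drop the Day 349 condition or reconcile it with the 8-day rule. Start the follow-up window the next day; at present last dose + 7 belongs to both windows for HbA1c.

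The cost is one extra window definition, one sentence and aligned numbers in one table. No new data are needed: the change uses whatever Week 52 values were collected.
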